- Vital signs: includes respiration rate (after two minutes supine rest), pulse, temperature, and blood pressure. On dosing days, at any time before drug administration.
- 12-lead ECG: 12-Lead resting digital electrocardiogram (ECG) are recorded digitally and in triplicate. ECGs will be performed at: Screening, Cycle 1 on Day 1, Day 8 and Day 15; Cycle 2 on Day 8 and Day 15; Cycle 3 on Day 1, Day 8, Day 15; Day 1 of Cycles 6, 9, 12 and every 12 weeks thereafter; also at EOT and first FUP. See Appendix 10.6 for schedule. ECGs to be taken: Pre-dose (-20 min. to -5 min. before administration of BI 836845 and/or enzalutamide) and immediately after the end of infusion of BI 836845 (up to 15 minutes after end of infusion). ECGs to be taken prior to PK sample time-points where applicable.
- 11. Safety labs: haematology, coagulation, biochemistry, electrolytes, urinalysis by dipstick before dosing. See section 5.2.5 for details.
- 12. Fasting glucose and HbA1C only at screening and Day 1 of each cycle and EOT.
- 15. CTC blood sampling prior to study drug administration at C1D1, C2D1, C3D1, C5D1, C7D1 and every 12 weeks thereafter, e.g. C10D1, C13D1 onwards and EOT. See section 5.1.2.3 and Appendix 10.6 for schedule.
- 16. PSA blood sampling at screening, C1D1 and from C3 D1 and Day 1 of every cycle thereafter.

Boehringer Ingelheim BI Trial No.: 1280.8 Doc. No.: c02304008-15 06 Jun 2022

Page 8 of 241

Trial Protocol Version 12

Proprietary confidential information. © 2022 Boehringer Ingelheim International GmbH or one or more of its affiliated companies. All rights reserved.

19. Tumour assessment: CT or MRI imaging of the chest, abdomen and pelvis at screening and prior to the start C3D1 onwards (see below) according to modified RECIST criteria (version 1.1) see appendix 10.4. If clinically indicated, imaging of any other known or suspected sites of disease using an appropriate method (CT scan and MRI) should be performed. After study entry, all lesions identified during the screening should be followed up at all specified imaging time points. The same radiographic procedure must be used throughout the study. See section 5.1.2.1

A bone scan should be performed at screening and prior to the start C3D1 and onwards according to schedule below.

Tumour assessment and bone scan will be performed at the following time points until progression/start of further anti-cancer therapy (assessments may be performed up to 7 days prior to the scheduled assessment date):

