6.1.2 Treatment Visits

The treatment phase of the study will start on the first day of infusion of BI 836845 in cycle 1. Administration of BI 836845 will be weekly and enzalutamide will be daily over a 28 day cycle of treatment in phase Ib and phase II of the study.

All treatment cycles will comprise of four visit days as per the Flow Chart Phase Ib and Phase II.

During the phase II randomised trial of the study from cycle 4 onwards patients on arm B (enzalutamide only) will only be required to attend for one visit per cycle on day 1 and when imaging assessments are scheduled; optional telephone contact calls may be included at day 8, day 15 and day 22 per cycle where required, and at the discretion of the investigator, for the collection of AE and concomitant medication information. For those patients receiving the combination treatment in any part of the trial, and who later discontinue BI 836845 permanently, they may attend only on day 1 of every cycle, from cycle 4 onwards, and when imaging assessments are scheduled.

For those patients that complete cycle 3 in phase Ib and phase II, these cycles will be repeated where clinical benefit is indicated. All assessments stated for cycle 3 in phase Ib and phase II will be repeated for all subsequent cycles, unless otherwise indicated in the Flow Chart.

Tumour assessments, including bone scans, will be performed as per the Flow Chart at week 8, week 16, week 24, week 36 and every 12 weeks thereafter. All tumour assessment visits may be within 7 days prior to the start of the respective cycle of treatment.

PK, biomarker assessments, PSA, CTC and immunogenicity sampling will be conducted for all days stated in the Flow Chart and Appendix 10.6.

No visit windows will be permitted on day 1 (visit 1) at the start of a cycle. On days 8, day 15 and 22 of every cycle a ± 1 day window will be permitted.

All planned visit dates are programmed from the start of day 1 (visit 1) of cycle 1. If a visit is missed there will be no re-scheduling; if a patient should attend the study site between the "missed" and scheduled visit, then the missed visit assessments should be performed. The current date and the reason for the delay must be noted in the medical records. All subsequent visits must adhere to the scheduled programme of visits for all cycles of treatment.

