	At C2D1, site staff must question the patient as to the date, time and dose of last enzalutamide intake prior to the visit; this information must be recorded in the eCRF.

Doc. No.: c02304008-15

Page 92 of 241

 $Proprietary\ confidential\ information. ©\ 2022\ Boehringer\ Ingelheim\ International\ GmbH\ or\ one\ or\ more\ of\ its\ affiliated\ companies.\ All\ rights\ reserved.$

	In Phase Ib expansion cohort only - Review of diary card and compliance check of enzalutamide taken 7 days prior to C2 D1.
Circulating tumour cells (CTCs)	As per the time-points on the Flow Chart and Appendix 10.6: Prior to study drug administration at C1D1, C2D1, C3D1, C5D1, C7D1 and every 12 weeks thereafter at C10D1, C13D1 onwards (until approval of protocol version 10).
Prostate Serum Antigen (PSA)	Single blood sample collected prior to dosing at C1D1, C3D1 and at the start of the cycle thereafter as per the Flow Chart.
Tumour assessments and bone scans	Every 8 weeks (every 2 cycles) up to week 24 and then every 12 weeks (every three cycles) thereafter from start of study treatment in phase Ib escalation and expansion cohort and from randomisation in phase II, i.e. within 7 days prior to theoretical C3, C5, C7, C10 and onwards. Following implementation of Protocol Version 12 as per standard of care.
	Assessment by modified RECIST criteria version 1.1 (R09-0262) and prostate cancer clinical trials working group (PCWG2) criteria, (R13-1642) see appendix 10.4 and section 5.1.2.1
Adverse event and concomitant therapy	Collection of data throughout study treatment period until after approval of protocol version 10 when only adverse event data will be collected.

Trial Protocol Version 12

Page 93 of 241

Proprietary confidential information. © 2022 Boehringer Ingelheim International GmbH or one or more of its affiliated companies. All rights reserved.

From cycle 3 onwards for phase Ib and phase II – the assessments and dosing schedule will be repeated for all subsequent cycles unless otherwise stated in the Flow Chart, e.g. tumour assessment schedule.

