In case there is no value within this timeframe (day 84 to 92), but the patient discontinued all treatments earlier than day 84, then the End of Treatment (EOT) value should be used. A PSA value will be taken as EOT value if the assessment was performed between the date of discontinuation of the last study medication until 7 days (included) after this date (according to the protocol schedule for the EOT visit (EOTV)).

In case there is no value within this timeframe (day 84 to 92), and the patient did not discontinue all treatments earlier than day 84, no earlier value will be taken as replacement, the assessment will be missing.

PSA response

PSA response is defined as a decline in PSA value >50% (with confirmation at least 3 weeks later) (R13-1642). See Section 5.1.2. for more details.

Changes in CTC response

Changes in CTCs will be evaluated using the following criteria:

- CTC reduction is defined as a decline in CTC value from ≥5 to <5 cells per 7.5mL blood (called "specimen volume" within this section and Section 7.5.2.3) (R14-0865), for at least one post-baseline time-point. Patients with a CTC value <5 cells per 7.5 mL blood at baseline, or with missing baseline value, are not taken into consideration for this endpoint.
- Maximum decline in CTC counts (in number of cells) compared to baseline that occurs at any point after treatment start, defined as the difference (absolute and percentage) between the minimum post-baseline CTC value and the baseline CTC value. Patients with missing baseline value are considered missing for this criterion.
- CTC status at week 12 (≥5 or <5 cells per 7.5mL blood)

Baseline value is the value collected before a patient starts treatment with trial medication. Patients with no post-baseline value are considered as missing for the three criteria.

For the criterion "CTC status at week 12", the nearest assessment to C4V1 (day 85) will be used, with following window:

- A later value, until one week after (day 92), can be used
- An earlier value, after four weeks in trial (day 29), can be used.

In case the patient discontinued the trial before the planned assessment, the EOT assessment will be used for this criterion in case it is the nearest to the target day.

In case it is needed for descriptive tables, multiple entries for one single time point in a patient will be assessed as follows:

- If only one valid value (with acceptable specimen volume or imputable value) is available, this one will be used

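### The SAP's 'CTC status at week 12' targets a visit with no scheduled CTC draw, so patients still on treatment mostly contribute a week-8 value

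*SAP*

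**What the plan says.** SAP 5.2.2.3 (Phase II, changes in CTC response) lists three CTC criteria. The third is whether the count is at least 5 or below 5 cells per 7.5 mL at week 12. For it, "the nearest assessment to C4V1 (day 85) will be used, with following window". The window reaches forward one week, to day 92. Looking back, "An earlier value, after four weeks in trial (day 29), can be used". For a patient who stopped before the planned assessment, "the EOT assessment will be used for this criterion in case it is the nearest to the target day".

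Protocol 6.2.2 schedules CTC samples as follows: "Prior to study drug administration at C1D1, C2D1, C3D1, C5D1, C7D1 and every 12 weeks thereafter at C10D1, C13D1 onwards". Footnote 15 of the Phase Ib flow chart agrees: "CTC blood sampling prior to study drug administration at C1D1, C2D1, C3D1, C5D1, C7D1 and every 12 weeks thereafter, e.g. C10D1, C13D1 onwards". The text of the matching Phase II footnote is not available in the public copy, so 6.2.2 is the source for Phase II. Neither list contains C4D1. The amendment log explains the origin: amendment 4 (September 2015) replaced the C4D1 draw with draws at C3D1 and C5D1. The SAP is dated September 2017.

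SAP 4.2 states that this criterion was not planned in the protocol. SAP 7.5.2.3 gives it a contingency table by arm, a 95% confidence interval and Fisher's exact test. SAP 7.9.4 names it as a potential surrogate for PFS or OS, to be examined only if PFS or OS is statistically significant.

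**The concern.** The label and target day describe a measurement that the schedule does not provide. The SAP refers to a planned assessment at C4V1, but no CTC assessment is planned there. A reader of the report would take week 12 at face value.

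The problem goes beyond naming. If the only routine way to obtain a value close to day 85 is an end-of-treatment draw, then patients who stop are measured near week 12 and patients who continue are measured at week 8 or earlier. The time of measurement then depends on discontinuation. This is also the only one of the three CTC criteria given a between-arm interval and test, and the one put forward for the surrogate analysis, where the timing of the marker matters.

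**Working it through.** **Inputs.** Cycle length 28 days (flow charts). Target day 85, window days 29–92 (SAP 5.2.2.3). CTC visits from protocol 6.2.2. Median PFS about 3 months on enzalutamide and 4.3–4.6 months on the combination (protocol 7.6).

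**Step 1: reproduce the SAP's days.** Day of CkD1 = 28 × (k − 1) + 1. C4D1 = 28 × 3 + 1 = 85; 85 + 7 = 92; C2D1 = 28 × 1 + 1 = 29. The SAP's three figures reproduce exactly.

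**Step 2: place the scheduled draws against the window.**

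| Visit | Day | Days from 85 | Within 29–92? |
|---|---|---|---|
| C1D1 | 1 | 84 | no |
| C2D1 | 29 | 56 | yes |
| C3D1 | 57 | 28 | yes |
| C5D1 | 113 | 28 | no |
| C7D1 | 169 | 84 | no |

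C3D1 and C5D1 are equally far from day 85. Even one day early, C5D1 is day 112, which is 112 − 92 = 20 days past the cap.

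**Step 3: which value is selected?**
- On treatment past day 92, draws on schedule: the C3D1 value, 85 − 57 = 28 days before the labelled time.
- The same patient with C3D1 missing or unusable: the C2D1 value, 85 − 29 = 56 days before.
- Stopped, with an end-of-treatment draw on days 58–92: that draw, because it is nearer to day 85 than day 57 is.
- Exceptions: under protocol 6.1.2, if a patient attends after a missed visit, "then the missed visit assessments should be performed", so a late C3D1 draw can fall nearer to day 85. A sample taken under the schedule before amendment 4 could be a true C4D1 value. The documents count neither.

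**Step 4: illustrative share still on treatment past day 92.** Assume exponential PFS and stopping only at a PFS event: S(t) = exp(−ln 2 × t / median), with t = (92 − 1) / 30.4375 = 2.990 months.
- Median 3.0: S = 0.501
- Median 4.3: S = 0.618
- Median 4.6: S = 0.637

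That is about 50% on enzalutamide and 62–64% on the combination. These are upper-end figures under this model. Patients also stop for other reasons (protocol 3.3.4.1). CTC endpoints use the CTCb set unless it differs by less than 5% from the randomised set (SAP 6.3). Samples of 5 to under 7.5 mL with a missing count or fewer than 10 cells are set to missing (SAP 7.5.2.2, applied to Phase II by 7.5.2.3).

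One assumption works the other way. If progression is found only at the week-8 and week-16 scans, the relevant share is S at day 57 (t = 56 / 30.4375 = 1.840): 0.654, and 0.743–0.758, before the same reductions.

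**The case against.** The strongest reply is that the rule is pre-specified, open about its look-back to day 29, and identical in both arms. The criterion is exploratory, protocol 7.2 bases inference on the size of observed differences rather than formal tests, and the surrogate analysis is conditional. SAP 7.5.2.3 plots every CTC assessment per patient, so actual timing can be seen. Because CTC is drawn less often than PSA, a longer look-back is a natural accommodation.

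Much of this stands, and it limits the weight of the point. It does not rescue the label. Disclosing the window does not tell the reader that the target day is unsampled, and a per-patient plot does not correct the tabulated proportions.

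The PSA comparison must be made carefully. A reader might infer that end-of-treatment substitution is peculiar to CTC. It is not: for PSA at week 12, if there is no value in the window "but the patient discontinued all treatments earlier than day 84, then the End of Treatment (EOT) value should be used". The difference lies with patients still on treatment, for whom "no earlier value will be taken as replacement, the assessment will be missing"; and PSA has a C4D1 draw, since the Phase II flow chart takes it on Day 1 of every cycle from cycle 3.

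A reader might also infer that every patient past day 92 contributes a week-8 value, or turn the shares above into counts out of 40 per arm. The documents support neither, because of the exceptions in Step 3 and the reductions in Step 4.

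**Conclusion.** The point holds and should be corrected, although no decision endpoint is affected. Under the current schedule, 'CTC status at week 12' has no draw at its target day. Apart from make-up draws and pre-amendment C4D1 samples, a patient on treatment past day 92 contributes the value from day 57, or from day 29 if that is missing. Values from days 58–92 come mainly from patients who stopped. The day arithmetic rests only on the protocol schedule and the SAP window. The shares passing day 92 rest on the exponential model and its assumptions and serve only to show that the affected group is not small.

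A reader might go further and infer a biased treatment comparison. The documents do not show one: the rule is the same in both arms, and neither the mix of sources by arm nor the effect of timing on CTC status can be derived from them. What they do show is a mislabelled landmark whose sampling time depends on discontinuation.

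**What to change.** 1. Stop calling the days 29–92 result week 12. Describe it as nearest to week 12 (days 29–92), and tabulate by arm the source of each value (C2D1, C3D1, C4D1 or make-up draw, end of treatment), the study day and the number missing.
2. Add the same contingency table, confidence interval and Fisher's test for CTC status at the scheduled C3D1 draw, labelled week 8, using only values in a narrow window around day 57, for example days 50–64. This compares patients at the same time. The downside is that some patients become missing, including any sampled only under the schedule before amendment 4. Relabelling as week 8 while keeping days 29–92 would not do, because day-29 and day-85 values would then be called week 8.
3. In SAP 7.9.4, state that the current schedule supplies no true week-12 CTC value for patients on treatment. The cited surrogate method is not in the documents, so the sponsor should confirm whether it can use a week-8 value before the analysis is run.

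The cost is SAP wording, one table and one extra display. No new data are needed.

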6.3 PATIENTS SETS ANALYSED

The following analysis sets will be defined for this trial:

• Enrolled set (ENR)

This patient set includes all patients with informed consent given. The enrolled set will be used for patient disposition tables.

• Treated set (TS)

This patient set includes all patients who are documented to have received and taken at least one dose of any study medication during the treatment cycles (from day 1).

In phase Ib escalation and expansion parts, the TS will be used for all planned safety and efficacy analyses, except for CTCs endpoints in phase Ib expansion part, for which the corresponding biomarker set (CTCb) will be used (see below). In phase II part, the TS will be used for all planned safety analyses.

• MTD Set (MS)

The MTD set defines the set of patients in the phase Ib escalation part of the trial that are fully evaluable for determination of the MTD in the first treatment course. The MTD set will be used for some safety analyses in the first part, this is specified in the technical TSAP.

Patients in the TS who were replaced within the MTD evaluation period in the first part of the trial will be excluded from the determination of the MTD. Replacement of patients in the first part of the study is defined in Section 3.3.5 of the CTP. The final list of replaced patients is supplied by the Trial Clinical Monitor (TCM) no later than the last report planning meeting (RPM) before the DBL for the safety analysis.

• Randomised set (RS)

This patient set includes all randomised patients in the phase II of the trial, regardless of whether or not they have received treatment. Patients are assigned to xentuzumab in combination with enzalutamide or enzalutamide alone. The randomised set will be used for the efficacy analyses of patients in the phase II of the study, except for CTCs endpoints, for which the corresponding biomarker set (CTCb) will be used (see below).

^[2] IPV will be identified via individual review at MQRM/RPM/DBL.

^{*} During the amendments of CTP the inclusion and exclusion criteria were adapted. Therefore, the inclusion/exclusion criteria valid at subject's enrolment have to be considered.

• Pharmacokinetic set (PKS)

This patient set includes all patients in the treated set who provide at least one PK parameter that was not excluded according to the description in Section 6.6.3 below. Thus, a patient will be included in the PKS, even if he contributes only one PK parameter value for one period to the statistical assessment.

Biomarker Sets

A patient set will be defined for each biomarker, if the data is available. These sets include all patients in the treated set who have at least one evaluable baseline value for a biomarker.

- BB: Blood Biomarkers Baseline measurements of free, dissociable and total IGF-1, free, dissociable and total IGF-2, total IGFBP-3 in serum and IGF bioactivity in heparin plasma
- o MSb: Mutational status of archival FFPE tumor samples, at baseline
- o mRNAS: Messenger RNA (mRNA) expression of IGF pathway related genes, e.g. tumor IGF-1 and IGF-2, at baseline
- o DCS: Relevant biomarkers related to IGF-1 and IGF-2 Downstream Cascade (e.g. pAkt) in tumour tissue, at baseline
- o PES: Protein Expression Set of IGF-1/2 in FFPE tumour sample, at baseline
- o CTCb: CTC baseline measurement

Biomarker sets will be used for the corresponding biomarker analyses, and the CTCb set will be used as well for the analysis of the secondary and further endpoints related to CTC assessments. In case one of the biomarker sets is identical or contains <5% difference in number of patients with the randomized set (or treated set in the phase Ib expansion part), then the randomized set (or treated set in the phase Ib expansion part) will be used and biomarker sets will not be considered at all.

• ECG Set (ECGS)

This patient set includes all patients in the treated set who do not have artificial cardiac pacemakers and have at least one on-treatment value for at least one ECG variable.

• ECG-PK Set

This patient set includes all patients in the ECG set who are

- o in the comparator group ('enzalutamide') or
- o in the 'xentuzumab+enzalutamide' groups and have at least one time-matching pair of valid xentuzumab plasma concentration and QTcF change from baseline (see Section 7.8.4).

The decisions whether

- o a concentration is considered valid or
- o a time deviation between PK blood sampling and ECG recording is acceptable will be made no later than at the final BRPM before DBL.

The analyses of ECG data will be based on the ECG set except those concerning the relationship between plasma concentrations and ECG variables which will be based on the ECG-PK set.

No per protocol population will be used for analyses.

TSAP for BI Trial No.: 1280.8

6.5 POOLING OF CENTRES

This section is not applicable because there are no inferential statistics, and therefore there is no statistical model in which centre/country can be included.

6.6 HANDLING OF MISSING DATA AND OUTLIERS

In general, missing data will not be imputed, unless required for the following analyses and definitions. Then the rules as described below apply.

Missing dates that affect the evaluation of endpoints specified in previous sections of this TSAP will be imputed utilising a "worst case" approach, which will be applied on a case-by-case basis (depending on the affected endpoint) and agreed to by the trial team members at the final BRPM before DBL at the latest.

The rules in the Table 6.6: 1 below have been agreed by the trial and project teams, and will be used in this trial, if applicable.

Table 6.6: 1 Rules for imputations of missing or incomplete dates

Date	Imputation rule		
Date of birth	In case only the year is given: 31 st of December		
Date of death	Date last known to be alive.		
	If only year and month are given: this will be imputed with 1 st of the month for the analysis of OS		
Date of first histological	1 st of month if day is missing		
diagnosis	1 st of January if month also missing		
Date of first appearance or	1 st of month if day is missing		
recurrence of metastasis	1 st of January if month also missing		
Date of start of concomitant medication	No imputation required		
Date of end of concomitant medication	No imputation required		
Date of start of subsequent anti-cancer therapy (imputation required only for censoring of PFS)	If the day (respectively day and month) of the start date of subsequent anti-cancer therapy is missing, then the first of the month (respectively 1st January) will be imputed unless this date leads to a date before the stop date of study medications. In this case, the study medications stop date + 1 day will be imputed.		
	Additionally, all imputed start dates of subsequent anti-cancer therapy should be before death date if available.		
Date of stop of subsequent anti-cancer therapy	No imputation required		

Table 6.6:1 Rules for imputations of missing or incomplete dates (cont.)

Date	Imputation rule
Date of end of treatment (only for patients still ongoing at time of snapshot/DBL)	Date of snapshot/DBL

6.6.1 **AEs**

Missing or incomplete AE dates are imputed according to BI standards (2).

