6.1.3.1 End of treatment visit (EOT)

The EOT visit will be performed after permanent discontinuation of trial medication (either BI 836845, or enzalutamide, whichever is the last drug to be taken) for any reason. The EOT assessment will then be performed as soon as possible (within 7 days), instead of the next planned visit.

Doc. No.: c02304008-15

Page 87 of 241

Proprietary confidential information. © 2022 Boehringer Ingelheim International GmbH or one or more of its affiliated companies. All rights reserved.

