Alive and not progressed, two or more consecutively missed radiological assessments	Censored	Date of last radiological assessment prior to missed radiological assessments
Progressed, zero or one missed radiological assessment prior to progression	Event	Date of radiological assessment of progression
Progressed, but two or more consecutively missed radiological assessments prior to progression	Censored	Date of last radiological assessment prior to missed assessment
Death but no progression, zero or one missed radiological assessment prior to death	Event	Date of death

Table 5.1.3: 1 Derivation rules for PFS (cont.)

Situation	Outcome (event or censored)	Date of outcome		
Death without progression, but two or more consecutively missed radiological assessments prior to death	Censored	Date of last radiological assessment prior to missed assessments		
Initiation of subsequent anti-cancer therapy				
Subsequent anti-cancer therapy started before progression or death	Censored	Date of last radiological assessment before subsequent anti-cancer therapy		
No baseline and post- baseline imaging and subsequent-anti cancer therapy started prior to a death	Censored	Date of randomisation (or first treatment administration, in non-randomised trials)		

Data will be carefully checked in order to detect missing assessments. In case further rules are needed, these will be discussed at a BRPM and added in a revision of the TSAP.

In order to identify that consecutive imaging time-points are missing for a given patient, a nominal time point [8, 16, 24, and then every 12 weeks thereafter] will be assigned to the assessments. This is achieved by creating windows for every assessment. The windows are defined in Table 6.7.2: 1.

Last evaluable imaging

An evaluable radiological image for the censoring of PFS is an image for which an overall response assessment of SD, Non-PD, Non-CR/Non-PD, PR or CR has been assigned. This is used for censoring of patients without progression at end of trial, or censoring prior to missed assessments or censoring prior to subsequent anti-cancer therapy. If the bone and the soft tissue assessment have been done at different dates, the date of the first assessment will be the date of censoring.

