5.2.2.3 Phase II

Progression-free survival (PFS) based on central review

The rules are the same as the ones described in Section 5.1.3, except the rule defined below. Instead of investigator assessment, the assessment based on central review will be used.

It should be referred to the imaging charter for more details regarding the assessment of response. However, there is one important change to RECIST 1.1 in the assessment of target lesions based on central review. In case one patient has the following:

- PR at last assessment
- more than 20% increase from nadir in the sum of longest diameters of target lesions, but less than 5 mm absolute increase from nadir.

In this case the assessment of PR should be carried forward to PR. This difference will not affect the endpoint PFS of this trial.

Overall survival (OS)

OS is defined as the time from randomisation until death from any cause.

For patients with 'event' as an outcome for overall survival:

• Overall survival [days] = date of outcome – date of randomisation + 1.

For patients with 'censored' as an outcome for overall survival:

• Overall survival (censored) [days] = date of outcome – date of randomisation + 1

The censoring rules for OS (i.e. outcome and date of outcome) are given in Table 5.2.2:3: 1.

Table 5.2.2.3: 1 Derivation rules for OS

Status at time of analysis	Outcome (event or censored)	Date of outcome
Patient died and the date of death is known	event	Date of death
Patient died and date of death is unknown	event	Date of last contact when the patient is known to be alive + 1 day
Patient alive	censored	Date of last contact when the patient is known to be alive
Unknown	censored	Date of last contact when the patient is known to be alive

The date when the patient was last known to be alive will be derived using the following data sources:

- Patient status: date of patient status obtained (if patient status is alive), last date patient known to be alive (in case patient is lost to follow-up), date of refusal (in case the patient actively refused to be followed up)
- Tumour assessment and/or radiological imaging data (date of imaging target lesions, date of imaging non-target lesions, date of detection of new lesion, date of assessment of bone lesions)
- Trial medication administration pages (including dates of start and end of administration, and termination of trial medication page)
- Onset and/or end dates of Adverse Events (AEs)

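### SAP Table 6.6:1 does not bound imputed dates by a documented progression or by the date last known alive, so a few PFS events can become censored and some deaths are dated too early

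*SAP*

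**What the plan says.** **New anti-cancer therapy (SAP 6.6, Table 6.6:1).** A start date with the day missing becomes the 1st of the month; with day and month missing it becomes 1 January. This applies "unless this date leads to a date before the stop date of study medications". The table continues: "In this case, the study medications stop date + 1 day will be imputed". The only other limit is that "all imputed start dates of subsequent anti-cancer therapy should be before death date if available".

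**Use of that date for PFS (SAP 5.1.3, Table 5.1.3:1).** The situation "Subsequent anti-cancer therapy started before progression or death" is censored, at "Date of last radiological assessment before subsequent anti-cancer therapy".

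**Scans after the last dose (Protocol).** Section 6.1.3.1 says of the end-of-treatment visit: "The EOT assessment will then be performed as soon as possible (within 7 days), instead of the next planned visit". The phase II flow chart asks for a scan at that visit whatever the reason for stopping, unless one was done in the previous 4 weeks. Section 5.1.2.1 continues scanning off drug until progression or further treatment.

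**Deaths.** Table 6.6:1 uses the date last known to be alive. It then adds: "If only year and month are given: this will be imputed with" the 1st of the month, for the OS analysis. Table 5.2.2.3:1 (SAP 5.2.2.3) gives, for a known death with unknown date, "Date of last contact when the patient is known to be alive + 1 day".

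**Safeguard.** SAP 6.6 opens with a general worst-case principle for missing dates, applied case by case and agreed no later than the final blinded report planning meeting (BRPM). It then says that the table's rules are agreed and will be used where applicable.

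**The concern.** An imputed date should not contradict something already known about the patient. Table 6.6:1 respects the drug stop date and the death date. It does not respect a progression scan made after drug stop, or a later contact at which the patient was alive.

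For PFS this touches the primary endpoint. A patient may stop drug for symptomatic progression or toxicity, show radiological PD at the end-of-treatment scan, and then start new treatment. If the new start date is partial, the imputed order can reverse the true order, and an investigator-documented event becomes a censoring at the preceding scan. This can happen only to patients who have already stopped treatment.

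For OS, a patient seen alive late in a month and recorded as dying in that month is given a death date before that contact. If randomised in the same month, the patient can get a negative survival time.

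Partial dates are foreseeable. Protocol 6.1.3.4 collects further treatment and death every 90 days, possibly by telephone, and Protocol 3.3.4.1 allows deaths to come from a public registry after withdrawal.

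**Working it through.** **1. The plan's own figure.** Protocol Table 7.6:2 gives the probability of an observed HR of at most 0.8 as Φ[(ln 0.8 − ln HR)/√(4/d)], with d events. At d = 60, √(4/60) = 0.258:
- HR 0.65: Φ(0.208/0.258) = 0.789 (stated 0.79)
- HR 0.70: Φ(0.134/0.258) = 0.697 (stated 0.70)
- HR 1.0: Φ(−0.223/0.258) = 0.194 (stated 0.19)

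The figures reproduce and are not in dispute.

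**2. The therapy rule on worked dates.** Imputed start = 1st of the month (or 1 January); if that is before drug stop, stop + 1 day. The event is lost if the imputed start is before the PD scan.

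| Drug stop | PD scan | True start | Recorded | Imputed | PFS |
|---|---|---|---|---|---|
| 5 Mar | 10 Mar | 20 Mar | March | 6 Mar | censored |
| 20 Feb | 10 Mar | 20 Mar | March | 1 Mar | censored |
| 5 Mar | 10 Mar | 20 Jun | year only | 6 Mar | censored |
| 5 Mar | 10 Mar | 20 Apr | April | 1 Apr | event kept |
| 5 Mar | 3 Mar | 20 Mar | March | 6 Mar | event kept |

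**3. Share lost, given a partial date.** Assumptions: drug stop on any day of a year, true start 1 to 28 days after the PD scan (mean 14.5), all equally likely. With PD 2 or more days after drug stop, an event is lost when therapy starts in the same month (or year) as the scan and the scan is not on the 1st (or 1 January).
- Day missing: 1 − 12 × 14.5/365 − 12/365 = 0.523 − 0.033 = 0.49
- Day and month missing: 1 − 14.5/365 − 1/365 = 0.960 − 0.003 = 0.96

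Full enumeration gives 0.491 and 0.958. PD on the day of drug stop loses nothing. PD one day after stop loses 3% with the day missing, because when the 1st is itself the stop date the floor does not apply.

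**4. Number of events.** The documents give no rates. Assume that 10–20% of 80 patients have PD documented after the last dose and that 10–20% of those have a partial therapy date: 80 × 0.10 × 0.10 = 0.8 to 80 × 0.20 × 0.20 = 3.2 patients exposed.
- Day missing: 0.49 × (0.8 to 3.2) = 0.4 to 1.6 events
- Month also missing: 0.96 × (0.8 to 3.2) = 0.8 to 3.1 events

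With 57 events instead of 60, the probabilities in step 1 become 0.783, 0.693 and 0.200. Each moves by about 0.006 or less.

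**5. The death rule.** The 1st of the month is early by (day of death − 1) days: 14.7 on average over a year, 30 at most. For deaths spread evenly over the year, the imputed date precedes the last date known alive in 93%, 74% or 51% of month-only deaths if that date was 1, 7 or 14 days before death. With a gap spread evenly over 0 to 90 days, the share is about 14.7/91 = 16%. A patient randomised on 15 March who dies in March gets OS = 1 − 15 + 1 = −13 days under the formula in SAP 5.2.2.3.

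**6. Wholly unknown death date.** Table 6.6:1 gives the date last known alive; Table 5.2.2.3:1 gives that date + 1 day. They differ by one day and cannot both be programmed.

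**The case against.** The strongest reply is that SAP 6.6 provides for case-by-case review before database lock, and that a death dated before a live visit, or a PD scan overridden by an imputed date, is the kind of conflict such a review would notice. That stands as mitigation. It does not remove the problem: the sentence names no check against progression or last contact, does not say which direction is the worst case, and is followed by specific rules that are to be used.

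The second reply is that few patients are exposed. The usual order is progression first, then stopping, and in that order the event is safe. The end-of-treatment scan is skipped if a recent one exists, and therapy start dates are a planned data item. This also stands, and it limits the size.

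Four stronger readings are tempting, but the documents do not support them:
- A reader might infer that every exposed patient loses an event. With only the day missing, about half do not, because therapy recorded in a later month than the PD leaves the event intact.
- A reader might infer that a year-only date discards every PD found after stopping. PD on the day after drug stop is kept when the stop + 1 floor applies.
- A reader might infer that the death rule also censors PFS. It does not; those deaths remain OS events.
- A reader might infer that PFS will exceed OS in one patient, because the month rule is limited to OS. The SAP does not clearly say how a month-only death is dated for PFS, so this is inference from silence.

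Nothing in the documents shows a difference between arms.

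**Conclusion.** The point holds as a defect in the stated rules, with a probably small effect. Table 6.6:1 can turn a documented progression into a censoring when PD is found 2 or more days after the last dose and the therapy start is partial. Under the assumed rates this affects about 0.4 to 3 of 60 events and moves the design probabilities by less than 1 point; the true number depends on the frequency of partial dates. The shares of about one half and nearly all rest on a therapy start 1 to 28 days after the scan; longer gaps would lower them.

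Month-only deaths are dated about 15 days early on average and 30 at most. They can precede the last contact or randomisation, and their handling for PFS is unclear. The one-day conflict for unknown death dates is real but trivial in size. The changes are worth making because the rules can produce wrong or impossible dates and the remedy is cheap.

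**What to change.** Change three lines of SAP Table 6.6:1:
- **Therapy start.** When the partial date is compatible with a start after a documented PD, impute the later of the current rule and PD date + 1 day, still before death. List these patients at the BRPM. In the first three rows of the table above, the start becomes 11 March and the event stays at 10 March.
- **Month-only death.** Impute the later of the 1st of the month and last known alive + 1 day, and use that date for both OS and PFS. A patient last seen alive on 20 March and recorded as dying in March is then dated 21 March, not 1 March.
- **Unknown death date.** Use last known alive + 1 day, as in Table 5.2.2.3:1.

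The cost is three table lines and one listing, with no new data. The first change has a small downside: the event is kept even if therapy truly began before the scan. Protocol 5.1.2.1 makes that order unlikely, because scheduled scanning ends when further treatment starts. Where outputs already exist, the same listing shows whether any patient was affected.
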